4.14. Study data collection procedure

The study will be collected according to the following plan:

Visit 1.

The visit takes place at the SS and is considered to be Day 1 of the study.

Having received the informed consent for participation in the study, the investigator evaluates the compliance of the volunteer with the inclusion criteria and verifies that he/she has no non-inclusion criteria.

During the visit, the investigator:

- Obtains the Informed Consent Form from the volunteers;
- Checks the inclusion/non-inclusion criteria, evaluates the volunteers with the help the Spielberger STAI. In case a volunteer has all the inclusion criteria and no signs that meet the non-inclusion criteria, the investigator performs further data collection and randomization;
 - Anthropometric data (weight, height and body mass index);
 - Evaluates vital signs (BP, HR, RR, and body t°);
 - Physical examination;
 - Collects demographic data (date of birth, gender);
 - Collects clinical data on concomitant diseases, therapy and records them;
 - Investigates the technology of virtual reality (Stages 1, 2, 3, and 4);
 - Evaluates the volunteers' complaints in terms of the development of adverse events/adverse device effect (AE/ADE);
 - Evaluates tolerability;
 - The clinician records all indicators collected at Visit 1 and transfers them to the CRF.

Visit 2.

The visit takes place at the SS.

During the visit, the Investigator:

- Checks the inclusion criteria. In case a volunteer has no signs that meet the exclusion criteria, the Investigator performs further data collection;
 - Evaluates vital signs (BP, HR, RR, and body t°);
 - Evaluated physical signs;
 - Investigates the technology of virtual reality (Stages 1, 2, 3, and 4);
 - Evaluates volunteers based on the Spielberger State-Trait Anxiety Inventory (STAI);
 - The investigator records all indicators collected at Visit 2 and transfers them to the CRF;
 - Evaluates the volunteers' complaints in terms of the development of adverse events/adverse device effect (AE/ADE);
 - Evaluates tolerability;
 - Informs volunteers on study completion.

4.15. Data management

Data collection and validation

Data will be collected using the CRF. Upon completion of the study, all filled CRFswill be provided to the CRO for data transfer into a spreadsheet and further statistical analysis. Data collection procedures and their verification will be described in detail in the operating procedures.

The investigator should submit information to the CRF on the day of the visit, but notlater than within 12 hours.

5. INCLUSION AND EXCLUSION OF THE SUBJECTS

It is planned to enrol approximately 160 healthy volunteers to the study for further randomization of 100 volunteers.

For the purposes of randomization the volunteers should meet the inclusion criteria and have no non-inclusion criteria, be familiar with the terms of participation in the study, and sign the Informed Consent Form for participation in the study.

5.1. Inclusion criteria for the study subjects:

The study will enrol healthy volunteers meeting all the following inclusion criteria:

1. Females and males 20-60 years old;
2. Volunteers have no history of cardiovascular diseases;
3. Volunteers have no essential abnormalities of the ECG;
4. Normal or moderate level of situational anxiety based on the Spielberger State-Trait Anxiety Inventory (STAI);
5. Signed Informed Consent Form for participation in the study.

5.2. Non-inclusion criteria for the study subjects:

The study will not enrol volunteers meeting one or more non-inclusion criteria:

1. Intolerance to the VR technology;
2. HR above 110 bpm or below 50 bpm;
3. RR above 23 breaths per minute;
4. Abuse of alcohol, psychotropic substances and narcotic agents;
5. Smoking more than 100 cigarettes a week;
6. Administration of medicinal products for the treatment of cardiovascular and nervous system diseases 3 days prior to participation in the study;
7. Drinking tonics and energy drinks for at least 2 hours prior to participation in the study;
8. Severe or acute forms of respiratory, urogenital, gastrointestinal, haematological, metabolic, endocrine, or neurological diseases;
9. Mental disorders, which, in the opinion of the investigator, may distort the results of the study;
10. Participation in any clinical study over the last 3 months prior to enrolment to the study;
11. Parkinson's disease, Parkinson's symptoms, tremor, restless leg syndrome, and other motility disorders;
12. Pregnancy;
13. Any disease of the thyroid gland.

5.3. Exclusion criteria for the subjects:

The study will not enrol volunteers meeting one or more exclusion criteria:

1. Emergence of any medical condition, an adverse event or circumstances when, in the opinion of the investigator, it is not in the best interests of the volunteer to proceed with the participation;
2. Failure to comply with the requirements of the protocol;
3. Onset of one of the non-inclusion criteria.

The reasons for the early withdrawal of the volunteer from the study are specified in the CRF. The discontinued patients will not be replaced.

5.4. Procedure of early withdrawal from the study

At any given time and for any reason, the Sponsor may decide to terminate or suspend the study early. Such decision will be brought to the attention of the investigator and the LEC in writing. Accordingly, in case the investigator decides to discontinue his/her participation in the study, he/she must promptly notify the Sponsor in writing. The authorized representative of the Sponsor or the CRO will inform the local Ethics Committee at the HCF.

6. STUDY SUBJECT INVESTIGATION

6.1. Procedure for use of the virtual reality technology

Depending on the results of randomization, the volunteers are assigned to Group 1 or Group 2:

Group 1: the volunteers will first be tested with the VR headset A, and during the next visit – with the VR headset B.

Group 2: the volunteers will first be tested with the VR headset B, and during the next visit – with the VR headset A.

Stages for each visit

Volunteers' tests during each visit consist of the following stages:

Stage 1, a volunteer lies down on the bed and 5-minute ECG is recorded at rest.

Stage 2, a volunteer undergoes the software-based "mental calculation" test while lying on the bed for 5 minutes. ECG is recorded simultaneously.

Stage 3, a volunteer lies down on the bed, puts on the VR headset, the investigator turns the program on for 5-minute exposure, ECG is recorded simultaneously.

Stage 4, a volunteer takes off the VR headset, lays on the bed for 5 minutes during which ECG is recorded, then the volunteer takes the Spielberger State-Trait Anxiety Inventory (STAI).

Thus, for each visit, 4 ECG will be registered for each volunteer: before the test, during the test, and after the test. Two assessments based on the Spielberger State-Trait Anxiety Inventory (STAI) will be carried out, as well: before the use of the virtual reality technology and after the use of the virtual reality technology.

6.2. Medicinal products allowed for use in the course of the study

Volunteers participating in the study may proceed with administration of medicinal products that are permanently used to treat concomitant diseases, having previously agreed their list with the investigator and provided they are not forbidden to use.

6.3 Medicinal products and food products prohibited for use in the course of the study

When a volunteer participates in the clinical study, it is prohibited to use the following groups of medicinal products. After Visit 2, the volunteers can take them in the event of prescription from a physician.

- medicinal product for the treatment of diseases of the nervous system (Code ATC-N);
- medicinal products for the treatment of diseases of the cardiovascular system (Code ATC-C).

In case a volunteer takes a prohibited medicinal product, he/she should be excluded from the study.

Volunteers are forbidden to consume tonics (tea, coffee, etc.) and energy drinks (Red Bull, etc.), and foods possessing a pronounced effect on the nervous and cardiovascular system. The minimal period after consumption of these foods to participation in the study is 2 hours.

6.4. Quality control and clinical monitoring

The monitoring procedures are in place to ensure that the rights of the volunteers are respected and the investigator conducts the study in accordance with the Protocol. Within the framework of this study, an on-site monitoring is planned.

During the study, a pre-scheduled visit of the monitor to the SS can take place. Its objective is to check data, monitor the correctness of obtaining volunteer consent, control over protocol guidelines and clinical study standards. During this visit, a check of the completeness of documents in the Investigator's File, verification of the availability of the signed Informed Consent Forms, verification of CRF will be performed.

Quality control will be implemented by skilled and trained personnel purposefully assigned for these tasks.

7. EFFICACY EVALUATION

7.1. Efficacy parameters

Principal and secondary parameters to be determined during the study:

Primary variable:

- Change in HF component after 5-minute exposure to the VR audio-visual sequence;

Secondary variables:

- Change in rMSSD after 5-minute exposure to the VR audio-visual sequence;
- Change in LF/HF ratio after 5-minute exposure to the VR audio-visual sequence;
- Change in SDNN after 5-minute exposure to the VR audio-visual sequence;
- Change in TP after 5-minute exposure to the VR audio-visual sequence;
- Change in HR after 5-minute exposure to the VR audio-visual sequence;
- Change in BP after 5-minute exposure to the VR audio-visual sequence;
- Change in Spielberger State-Trait Anxiety Inventory (STAI) score after 5-minute exposure to the VR audio-visual sequence.

The criterion for the prevailing efficiency for each variable is the presence of statistically significant differences between groups in favour of any of the groups with a directivity, which indicates the effectiveness of the technology. Procedures and methods required for efficacy evaluation are described in Section 4.13. The time and events schedule is shown in Section 4.12.

8. SAFETY AND TOLERABILITY EVALUATION

Detection and registration of AR/ADE

In the course of the study, beginning with the moment of putting the virtual reality headset on the volunteers, registration of AR/ADE will be carried out by carefully monitoring the health of each of them.

To this end, during each visit, the investigator asks the volunteers questions related to their well-being, conducts physical examination, evaluates vital signs (blood pressure, heart rate, and body temperature).

Diseases, signs or symptoms, results of electrocardiography that are not compliant with the normal values and were observed in the volunteer prior to the beginning of the study are not considered to be adverse reactions if they were detected during the trial (except for cases when there was a deterioration in the severity or frequency of manifestations).

Adverse reactions occurring when the virtual reality technology is applied are described in Section 2.2. of this Protocol.

In the event of any symptoms of AR/ADE, the volunteers should immediately report this to the investigator. Volunteers should report any undesirable events, regardless of whether they are related to the virtual reality technology (from the perspective of the volunteer).

The following should be classified as AR/ADE:

- exacerbation of concomitant diseases;
- an increase in the frequency or severity of previous diseases, or episodic events;
- the disease detected or diagnosed after the introduction of the virtual reality technology, even if it is possible that the disease was pre-existing prior to the volunteer's participation in the study;
- prolonged, persistent diseases or symptoms that were detected at the initial stage and the severity of which increased after the volunteer started taking part in the study;
- clinically significant disorders detected by the results of electrocardiography or other surveys after the introduction of the virtual reality technology, or those that were observed at the initial stage, and the severity of which increased against the background of the use of the virtual reality technology.

The following should not be classified as AR/ADE:

- diseases or conditions detected or diagnosed before the beginning of the use of the virtual reality technology, the severity of which has not increased;
- situations in which there is no adverse event, from a medical point of view (e.g., hospitalization due to scheduled surgery);
- any clinically significant laboratory deviations that was detected before the first application of the virtual reality technology.

All cases of AR/ADE observed by the volunteers and/or the clinician during the study, including events not directly related to the virtual reality technology, should be recorded in the appropriate section of the CRF.

Information about AR/ADE should include: date and time of beginning and ending, nature of manifestations, severity, likelihood of connection with the virtual reality technology, measures taken to eliminate AR/ADE, seriousness, resolution of the event/reaction. In addition, these data should be provided in the final Clinical Study Report.

The investigator should notify the Sponsor of the study of all AR/ADE. The Sponsor is required to provide complete information about all AR/ADE registered during the clinical study in the Clinical Study Report.

The relationship between AR/ADE and the investigational virtual reality technology

In this study, the following definitions are used in accordance with the Guidelines on medical devices. Clinical Investigations: Serious adverse event reporting. Under Directives 90/385/EEC AND 93/42/EEC

Adverse reaction (AR) is any adverse manifestation, unpredictable disease or injury, or any undesirable clinical signs (including laboratory abnormalities) in the subject, users or other individuals, regardless of their association with the investigational medical device. [20]

Adverse device effect(ADE) – side effect associated with the use of the investigational medical device. [20]

AR/ADE are classified as serious and non-serious.

A serious adverse device effect (SADE) or a serious adverse event is any adverse medical event that results in:

- a) led to a death, injury or permanent impairment to a body structure or a body function.
- b) led to a serious deterioration in health of the subject, that either resulted in:
 - a life-threatening illness or injury, or
 - a permanent impairment of a body structure or a body function, or
 - in-patient hospitalization or prolongation of existing hospitalization, or
 - in medical or surgical intervention to prevent life threatening illness
- c) led to foetal distress, foetal death or a congenital abnormality or birth defect

Planned hospitalization for pre-existing condition, or a procedure required by the Clinical Investigation Plan, without a serious deterioration in health, is not considered a serious adverse event.

Non-serious AR/ADE – all undesirable reactions that do not meet the above criteria.

ADE are also classified as unanticipated and anticipated.

Unanticipated Serious Adverse Device Effect (USADE) Serious adverse device effect which by its nature, incidence, severity or outcome has not been identified in the current version of the risk analysis report.

Anticipated SADE (ASADE): an effect which by its nature, incidence, severity or outcome has been previously identified in the risk analysis report

Causality assessment

The relationship between the use of the medical device and the occurrence of each adverse event shall be assessed and categorized. During causality assessment activity. The presence of confounding factors, such as concomitant medication/treatment, the natural history of the underlying disease, other concurrent illness or risk factors shall also be considered. The above considerations apply also to the serious adverse events occurring in the comparison group For the purpose of harmonising reports, each SAE will be classified according to five different levels of causality. The sponsor and the investigators will

use the following definitions to assess the relationship of the serious adverse event to the investigational medical device or procedures.

Table 4. Categories and criteria for determination of the causal relationship

Degree of probability	Manifestation
Not related:	Relationship to the virtual reality technology is excluded
Unlikely	The relationship with the use of the virtual reality technology seems not relevant and/or the event can be reasonably explained by another cause, but additional information may be obtained.
Possible	The relationship with the use of the virtual reality technology is weak but cannot be ruled out completely. Alternative causes are also possible (e.g. an underlying or concurrent illness/ clinical condition or/and an effect of another device, drug or treatment). Cases were relatedness cannot be assessed or no information has been obtained should also be classified as possible.
Probable	The relationship with the use of the virtual reality technology seems relevant and/or the event cannot reasonably explained by another cause, but additional information may be obtained.
Causal relationship:	The serious event is associated with the virtual reality technology beyond reasonable doubt.

Determination of the severity of AR/ADE

The severity of adverse reactions is evaluated on the basis of the Common Terminology Criteria for Adverse Events (CTCAE), version 4.0.

Table 5. AR/ADE severity evaluation criteria

Degree	Evaluation criterion
1	Low-severity AR/ADE (insignificant, do not require medical intervention, asymptomatic disorders, which are determined by the results of laboratory diagnostics and have no substantial clinical significance)
2	Moderate AR/ADE (require minimal intervention from a physician)
3	Severe AR/ADE (significant symptoms requiring hospitalization or invasive intervention)
4	Life-threatening or disabling AR/ADE (complicated by acute, life-threatening conditions, require intensive care or invasive procedures)
5	AR/ADE with a fatal outcome

Categories of AR/ADE outcomes and their definition

- **The event has resolved without consequences** – there are no symptoms and the volunteer is not treated to eliminate **AR/ADE**.
- **Stabilization of condition** – the outcome of AR/ADE is classified as stabilization of condition, according to the investigator's assessment.
- **The event has resolved with consequences** – the event was reversed, but its consequences remained: as a result of AE/AR the volunteer experienced a temporary or permanent disability/inability to work. Any AE/AR that have resolved with consequences are classified as serious AE/AR.
- **The event has not resolved** – symptoms persist.
- **Death of a volunteer.**

Actions to be taken after development of AR/ADE

The investigator should keep records of measures taken and consequences for each case of AR/ADE based on the following criteria:

- no actions were performed;
- treatment prescription;

- hospitalization;
- termination of application of the virtual reality technology;
- cancellation of application of the virtual reality technology;
- resuscitation measures (in cases of development of life threatening AR/ADE).

The investigator should monitor changes in the development of clinical manifestations over time, as well as provide information to the Sponsor in accordance with the requirements of the Protocol.

In case of serious unpredicted AR/ADE, provide information to the study Sponsor and the Ethics Committee at the SS.

Measures taken in cases of development of AR/ADE

In case of AR/ADE, the investigator should take medical measures and actions aimed at their reversal. In the event of the occurrence of AR/ADE health-threatening and/or life-threatening for the volunteer, the investigator is allowed to unblind the randomization code making a telephone call to the study monitor or to another employee of the Sponsor or the CRO ([contact]). The reason for disclosure of the code should be described in detail in the CRF.

All volunteers, who had registered AR/ADE during the study period, should be monitored until their resolution or achievement of clinical stability.

Observation of the volunteers who have suffered from AR/ADE, should continue until complete recovery or determination of the causes of its occurrence. All attempts to obtain additional information should be documented.

The investigator is responsible for all the therapeutic measures and final procedures.

Reporting about AR/ADE

All cases of AR/ADE observed by the investigator or spontaneously reported by the volunteers during the study, including events not directly related to the virtual reality technology, should be recorded in the appropriate section of the CRF.

The Investigator should provide full description of AR/ADE, the degree of severity, the date and time of the beginning and end of the event, the pharmacotherapy, study outcomes, describe the measures for the elimination of AR/ADE, and their consequences. In addition, these data should be provided in the final Clinical Study Report.

The investigator should notify the Sponsor of the study of all RE/ADE with respect to the confidentiality of data: in the primary and subsequent messages, the volunteers are identified by their identification (randomization) numbers, initials and date of birth.

9. STATISTICS

9.1 Justification of the sample size

The required sample size is the minimum sufficient number of subjects to obtain clinically and statistically significant outcomes of the clinical trial. Depending on the type of clinical trial and its design, as well as the types of variables used to evaluate the treatment effect, the sample size may vary.

The sample size depends on the following parameters:

- The size of the clinically significant differences (δ);
- Limiting probability of type I error α (usually for the tests of the prevailing efficiency is equal to 0.05 or 5% (two-tail));
- Limiting probability of type II error β (usually equal to 0.2) and, respectively, the power (80 %);
- Estimated on the basis of previous studies of intrasubject variability.

This study is designed to prove the superiority of the use of VR headset A vs. the use of the VR headset B for the main variable — “Change in HFcomponent after 5-minute exposure to the audio and visual VR sequence”.

To estimate the sample size, it is assumed that the following statistical hypotheses are verified for the demonstration of superiority under conditions of the single-group design:

$$H_0: \varepsilon \leq \delta \text{ vs. } H_a: \varepsilon > \delta, \quad (1)$$

where δ — the limit of superiority — the marginal value of the clinically significant differences in which it can be assumed that the investigational device (VR headset A) is superior to the comparable device (VR headset B);

$$\varepsilon = \mu_A - \mu_B \quad (2)$$

true difference between the arithmetic mean of the results obtained using the VR headset A and the VR headset B.

According to Chow et al [18], the sample size can be estimated using the following expression:

$$n = \frac{(z_{\alpha} + z_{\beta})^2 \sigma_m^2}{2(\varepsilon - \delta)^2} \quad (3)$$

where d — the size of clinically important differences as determined by experts; a — limiting probability of type I error (significance level), which in most cases is equal to 0.05 (5%); b — limiting probability of type II error; s_m — coefficient of variation, which is evaluated based on the results of previous studies.

In this study, the size of the clinically important differences d is 0.1 (10%), $a = 0.05$ (two-tailed), $b = 0.05$ (study power of 95 %). It is assumed that the difference e will be 0.25 (25 %), and s_m will be 0.35 (35 %). The results of calculations are given in the table below:

Statistical parameter	Value
a — limiting probability of type I error	0.05
b — limiting probability of type II error	0.05
Percentage point of the standardized normal distribution for a	1.96
Percentage point of the standardized normal distribution for b	1.64
Difference in means e	0.25
The value of clinically significant differences d	0.1
Intrasubject variability s_m	0.35
Estimated sample size	36

Thus, it is necessary to enrol 36 volunteers to this study, according to the calculations. Yet, given that a large proportion of volunteers may not meet the inclusion criteria or non-inclusion criteria, and are the non-responders, at least 80 volunteers should be enrolled to the study. Yet, since it is planned to conduct the study of the virtual reality effect separately for different groups of volunteers, it is recommended that approximately 160 volunteers are included to get 100 randomized volunteers.

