4.3. Description of randomization and blinding

In order to observe the “blindness”, the study group of each volunteer will be determined in accordance with their randomization group.

The blind study suggests volunteers’ lack of information about used VR technology. VR headsets will be labelled as A and B, and the volunteer will not be aware of the corresponding technology. Unblinding will take place upon completion of the study.

With a view to a more even distribution of the volunteers, a block randomization design (fixed-length blocks of 10 volunteers balanced by groups) will be used.

Randomization is carried out only after the signing of the Informed Consent Forms and verification of the volunteers’ compliance with all inclusion/non-inclusion criteria (the volunteers are assigned with randomization numbers).

In practice, the implementation of the developed randomization scheme will be carried out using numbered envelopes provided by the Sponsor to the site. Each envelope will contain 10 randomization cards. The investigator will open an envelope and randomly take out randomization cards, which will say “Group 1” or “Group 2”, according to which the volunteers will take part in the study.

The next envelope will be opened as the investigator runs out of randomization cards in the previous envelope in ascending order of the numbers on envelopes.

The distribution by groups is given in Table 2.

Table 2. Distribution of healthy volunteers

	Group 1	Group 2
Number of volunteers	50 healthy volunteers	50 healthy volunteers

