4.9. Disclosure of randomization code

Information related to decoding of randomization codes will be retained by the Sponsor throughout the study. Disclosure of randomization codes will be carried out after the Sponsor receives statistical data on the findings and outcomes of the study.

An Authorized Representative of the Sponsor retains confidentiality of randomization codes and cannot disclose them directly or indirectly to volunteers or other parties/individuals/entities.

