9.2.3 Efficacy analysis

Efficacy analysis based on quantitative variables

For each quantitative parameter, estimate its relative change after the exposure of the headset in comparison with the values before its exposure in % compared with the baseline using the following formula:

$$X(\%) = \frac{T_{\text{нiсiя}} - T_{\text{до}}}{T_{\text{до}}} \times 100\% \quad (3).$$

Give descriptive statistics values (n, arithmetic mean, median, standard deviation, minimum and maximum value) for each time point, grouping the data separately for each headset, and, also, show the difference between these indicators for each headset (“after” – “before”), and between the headsets (“VR headset A” – “VR headset B”). Present changes of the parameters over time graphically.

To analyse the efficacy of the four-factor dispersion analysis (ANOVA) based on the mixed model: the “exposure sequence” factors (levels “A – B” and “B – A”, “exposure period” (levels: “Period 1” and “Period 2” and “headset” (levels: “VR headset A” and “VR headset B”) are fixed, the “subjects” factor is random, distributed in the “exposure sequence” factor followed by the use of contrast analysis between the levels of the “headset” factor (level “VR headset B” – reference).

Check the normal distribution of the ANOVA residues using the Shapiro-Wilk test. In case the residues are not distributed normally, perform the ANOVA on ranks [19].

Efficacy analysis based on categorical variables

Calculate the descriptive statistics parameters (frequency and proportion in percentage).

Present results graphically.

To compare the proportions for the “VR headset A” and the “VR headset B” McNemar’s test should be used. In case the categorical variable has more than two categories, the marginal frequency test should be used.

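### Section 9.1 prints which headset letter is the investigational device, a key that 4.9 and Section 8 most plausibly treat as withheld, so the protocol does not settle whether the investigator is blinded

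*Protocol*

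**What the plan says.** - **Section 9.1** gives the aim as "This study is designed to prove the superiority of the use of VR headset A vs. the use of the VR headset B" and defines the margin as the difference at which it can be assumed that "the investigational device (VR headset A) is superior to the comparable device (VR headset B".
- **Sections 4.4 and 4.8** put the letters A and B on the two physical headsets. Neither says which one carries the Pure Purr software.
- **Section 9.2.3** sets the contrast with "level “VR headset B” – reference". This agrees with 9.1 but does not by itself reveal which device is which.
- **Section 4.3** describes the blind in terms of volunteers only: "VR headsets will be labelled as A and B, and the volunteer will not be aware of the corresponding technology". The title says blinded, without saying single or double.
- **Section 4.3** also says "The investigator will open an envelope and randomly take out randomization cards", each marked Group 1 or Group 2. Sections 4.2 and 6.1 print the headset order for each group, and 4.8 has the investigator log the group and the headset letter used.
- **Section 4.9** leaves the decoding information with the Sponsor, whose representative "cannot disclose them directly or indirectly to volunteers or other parties/individuals/entities". On timing: "Disclosure of randomization codes will be carried out after the Sponsor receives statistical data on the findings and outcomes of the study".
- **Section 8** provides that, in a health- or life-threatening event, "the investigator is allowed to unblind the randomization code making a telephone call", with the reason entered in the CRF.
- **Sections 12.4 and 11** have the investigator agree in writing to work to the protocol and have site staff review it at the initiating visit. Section 12.4 also bars passing its contents to others without the Sponsor's written consent.

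**The concern.** A procedure for withholding and releasing a code makes sense only if the person asking for it does not already have it. Here the protocol sets up such a procedure for the investigator and also prints, in its sample-size section, what appears to be the code.

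What is at stake is the standing of the outcomes that depend on the investigator's judgement: the 5-point tolerability rating (4.1, 4.14), the causality assessment of adverse events (Section 8), withdrawals decided on the investigator's opinion (5.3) and, where 4.13 applies, delivery of the mental-calculation stressor. Knowledge of the arm creates an opportunity for bias in these. As the text stands, a reader cannot tell whether they are meant to be assessed blind.

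**Working it through.** **The section's own figure.** With z values 1.96 and 1.64, variability 0.35, assumed difference 0.25 and margin 0.10, the formula in 9.1 gives n = (1.96 + 1.64)² x 0.35² / (2 x 0.15²) = 12.96 x 0.1225 / 0.045 = 35.28, which rounds up to the stated 36. The figure is not in dispute and does not change with this point. It does confirm that A minus B in 9.1 is a directed difference between named devices, not neutral notation.

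**Step 1: what the investigator knows without 9.1.** The group comes from the card (4.3), the order of the letters from the group (4.2, 6.1), and the letter in use at each session from the headset label and the use log (4.4, 4.8).

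**Step 2: what is left to withhold.** Section 4.9 never defines the randomization code. For a volunteer already allocated, the group, the order and the letter are all known to the investigator. The list of future allocations is of no use in an emergency call about that volunteer. What remains is which letter is Pure Purr and which is sham.

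**Step 3: whether 9.1 supplies it.** It does, in words and with the letters used on the devices. With Step 1, the arm can be deduced at every session.

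**Step 4: the sections under each possible intent.**
- *Single-blind, volunteers only.* Sections 4.3 and 9.1 are consistent. The ban in 4.9 on telling any other party and the telephone step in Section 8 have no purpose.
- *Investigator also blinded.* Sections 4.9 and 8 make sense. Section 4.3 is incomplete and 9.1 defeats the arrangement.

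Neither intent fits all four sections.

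**Step 5: reach.** Headset sessions: 100 volunteers x 2 visits = 200. Tolerability ratings: 100 x 2 = 200 if made at each visit (Table 3, 4.14), or 100 x 1 = 100 if made once after Visit 2 (4.1). These count exposure, not bias.

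**Step 6: whether the analysis can be run on coded letters.** For the two-sided contrast in 9.2.3, exchanging the letters reverses the sign and leaves the test unchanged. The hypothesis in 9.1 is different, because it is directional against a margin of 0.1. At the planning value the difference is +0.25, which is 0.15 beyond the margin. With the letters exchanged it is -0.25, on the null side. That conclusion cannot be drawn until the letters are decoded.

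**The case against.** The strongest case on the other side has four parts.

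1. *The only explicit statement of the blind is not breached.* Section 4.3 speaks of volunteers, and no section says in terms that the investigator is blinded. This stands. A reader might infer that the protocol promises a double-blind study and then breaks it, but the documents do not say that. What remains is the conflict with 4.9 and Section 8, which 4.3 does not resolve.
2. *The randomization code is never defined as the A/B key.* This also stands, so the reading in Step 2 is an inference. It is the most reasonable one, because nothing else about an allocated volunteer is unknown to the investigator.
3. *Section 9.1 is not the only route to the arm.* Section 2.1 describes how the sham differs and has separate figure captions for the two versions, and the investigator starts the program (6.1). Staff may recognise the content whatever the letters are. This limits what any relabelling can achieve.
4. *The consequences are limited.* HF is derived from a recorded ECG, and the volunteer completes the STAI. Section 9.2.4 plans descriptive statistics only for safety and tolerability. The causality definitions are worded for serious events and are shared with the Sponsor, who holds the code anyway. The stress test is read aloud in 4.13 but called software-based in 6.1, and 4.13 gives all volunteers the same number sets. All of this stands and keeps the point modest.

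A reader might also infer that the volunteers' blind is lost because the key is in print. Section 12.4 bars passing on the protocol's contents, and nothing shows that a volunteer would see 9.1.

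**Conclusion.** The point holds as an internal inconsistency. Section 9.1 discloses the device identity to every holder of the protocol, while 4.9 and Section 8 are written as though that identity were withheld from the investigator, and 4.3 is silent on the investigator.

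This rests on three assumptions: that the code in 4.9 and Section 8 is the A/B identity, that the letters in 9.1 are those on the physical headsets, and that site staff receive the protocol with 9.1 in it (supported by 11 and 12.4).

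The size can be given only as reach: 200 planned sessions, and 200 or 100 tolerability ratings depending on which section governs. Neither the size nor the direction of any bias can be derived. It would go too far to conclude that the HF result is biased. The variable is largely, though not fully, shielded, since the stressor before the exposure may be delivered by someone who can know the arm.

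**What to change.** Reconcile 4.3, 4.9, Section 8 and 9.1 according to which design is intended.

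**If the investigator is meant to be blinded:**
- In 9.1, write *investigational* and *sham* in place of headset A and B.
- Assign the physical letters by a concealed draw, with the key held off site.
- State in 4.3 that the investigator is blinded to the A/B identity.
- Run the 9.2.3 contrast on the coded letters, and say that the directional conclusion against the 0.1 margin is drawn only after decoding.

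**If a single-blind study is intended:** say so in the title and 4.3, bring 4.9 and Section 8 into line, and report the investigator-rated outcomes as unblinded. The letters in 9.1 may then stay.

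**Cost.** The first option needs text edits and new labels on two headsets. The second needs text edits only. Neither adds staff, visits or volunteers, but either needs an amendment agreed with the parties listed in 12.3.

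**Limits of the first option, to be stated in the protocol.** Staff may still recognise the content (2.1, 6.1). With only two headsets, a single emergency unblinding reveals the key for all past and future sessions.
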